10.3. Institutional review board (IRB)/Independent ethics committee (IEC)

There must be prospective approval of the study protocol, protocol amendments, and other relevant documents (e.g., informed consent forms if applicable) from the relevant IRBs/IECs. All correspondence with the IRB/IEC must be retained. Copies of IRB/IEC approvals must be forwarded to Pfizer.

We will obtain a customized HIRA database between 1 Mar 2012 and 31 Dec 2019. This study was approved by the Sungkyunkwan University's Institutional Review Board (SKKU-IRB-2020-12-010), which waived the requirement for informed consent.

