5. INTRODUCTION

Venous Thromboembolism (VTE), which includes deep vein thrombosis (DVT) and pulmonary embolism (PE), is a major cause of morbidity, mortality and healthcare expenditure. Although the occurrence of VTE in the Asian population has been lower than in Western populations, Its incidence has been reported to have increased rapidly in recent years.

For pharmacologic treatment of patients with VTE without cancer, the American College of Chest Physicians (CHEST) guidelines recommend the use of Non-Vitamin K antagonist oral anticoagulants (NOACs) over Vitamin K Antagonists (VKAs), with supporting evidences suggesting that each NOAC (e.g., apixaban) is effective at preventing recurrent VTE. In more recent treatment guidelines for the management of VTE released by the American Society of Hematology (ASH), NOACs are still recommended over VKAs for the initial management of VTE. NOACs are classified as new generation of anticoagulants with approved indications of the risk reduction of stroke and embolism in nonvalvular atrial fibrillation (NVAF) as well as prophylaxis and treatment of DVT and PE.

All NOACs became available as the first-line treatment of acute VTE in Korea after reimbursement expansion in May 2015. However, despite the increasing use of NOACs among VTE patients, there are still limited real-world evidence that assess treatment patterns as well as effectiveness and safety of the different anticoagulants especially among Asian population.

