7. DATA SOURCES

We will use the nationwide HIRA database of South Korea between 1 Mar 2012 and 31 Dec 2019 to identify all variables (exposure, outcome, covariates) needed to conduct this study. The HIRA database includes healthcare utilization information of residents of South Korea, with patient identifiers anonymized. Information on age, sex, diagnosis (ICD-10 diagnostic code, date of diagnosis, setting of diagnosis [inpatient, outpatient, emergency department], and others), medications dispensed/prescribed (national drug chemical code based on the active ingredient, date of prescription, days' supply, dose, route of administration, and others). Previous validation study that compared diagnosis codes recorded in the HIRA to those of recorded in electronic medical records found an overall positive predictive value (PPV) of 82.3%.

[figure not shown]

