8.2. Study population

The study cohort will be defined as patients diagnosed with VTE between 1 Mar 2013 and 30 Jun 2019. The cohort entry will be defined as the date of incident VTE diagnosis. The index date will be defined as the date of first prescription for anticoagulants within 30 days after the index VTE event. The length of the exclusion assessment window will vary depending on the condition, from 12-months at minimum to anytime prior to index date. The following patients will be excluded: A record of VTE diagnosis within the 12-month period prior to the index VTE encounter, diagnosed with atrial fibrillation, atrial flutter, mechanical heart valve replacement or mitral stenosis anytime prior to index date, had a record of Inferior Vena Cava filter anytime prior to index date, received anticoagulatory therapy within the 12-month period prior to index VTE encounter to restrict to new users of anticoagulatory therapy, prescribed two different anticoagulants on the same index date to prevent exposure misclassification, had a record of pregnancy within the 9-month period prior to index date, and for the Phase II of the study only, had a record of active cancer within six months period prior to index date.

Baseline sociodemographic characteristics (e.g., age, sex) will be assessed on the index date, whereas clinical characteristics (comorbidities, previous use of medications, Charlson comorbidity index [CCI], HAS-BLED scores, initial presentation of VTE, number of outpatient visits) will be assessed in the 6-month period prior to the index date except when otherwise specified in section 8.4 *Variables* (Figure 2).

Within this study cohort, we will describe the treatment patterns of anticoagulants prescribed for VTE treatment throughout the period of follow-up, defined as the period from the index date to the end of the study period. Moreover, if feasible, we will also examine the risk of major bleeding overall and by site, associated with each NOAC use, as compared with warfarin.

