- If a patient has evidence of a repeat prescription within 30 days of the end of their prescription and does not experience any of the above events (treatment interruption, switch, or discontinuation), they will be assumed to be persistent on treatment.[1]
- Clinical event preceding first treatment change will be defined as occurrence of any event listed below within 30 days before treatment interruption, switch, or discontinuation. A new clinical event will be considered 'new' when it occurs for the first time within a 6-month period for acute conditions (arterial thromboembolism, ischemic stroke, transient ischemic attack, myocardial infarction, angina pectoris, acute kidney injury, and abnormal liver function) and 5-years for chronic conditions (cancer, chronic kidney disease, and liver disease). A patient may contribute to multiple events.
 - ① Major bleeding (as defined in Phase II)
 - ② Complications of VTE: post-thrombotic syndrome and chronic thromboembolic pulmonary hypertension
 - ③ Thromboembolism: PE diagnosis in patients with index event as DVT only, new diagnosis of arterial thromboembolism, ischemic stroke, transient ischemic attack, myocardial infarction, or angina pectoris
 - ④ Major surgery: orthopedic surgeries (knee arthroplasty, hip arthroplasty, and hip fracture surgery), cancer surgeries (stomach, colorectal, hepatobiliary, pancreatic, breast, ovarian, cervical, renal, bladder, prostate, lung, and esophageal cancers, and brain tumors), and benign surgeries (myomectomy, oophorectomy, and transurethral resection of the prostate)
 - ⑤ Cancer-related event (among non-active cancer patients only): new diagnosis of active cancer
 - ⑥ Kidney function change: new diagnosis of chronic kidney disease or acute kidney injury
 - ⑦ Liver function change: new diagnosis of liver disease or abnormal liver function

Clinical event preceding first treatment change	ICD-10 diagnosis code
Major bleeding	Defined in Phase II
Complications of VTE	
Post-thrombotic syndrome	I87.0
Chronic thromboembolic pulmonary hypertension	I27.2
Thromboembolism	
PE diagnosis	I26.0, I26.9
Atrial thromboembolism	I74
Ischemic stroke	I63
Transient ischemic attack	G45.9
Myocardial infarction	I21
Angina pectoris	I20
Major surgery	
Orthopedic surgeries	N0305, N0601, N0611, N0641, N0711, N2070, N0715, N2710, N0731, N0981, N0991, N1711, N3710, N1721, N3720, N1715, N4710, N1725, N4720, N2072, N2077, N2712, N2717, N3712, N3717, N3722, N3727, N4712, N4717, N4722, N4727

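### The 5-year look-back that makes a chronic condition 'new' is not in the data for any event before 1 March 2017, so what counts as new shifts with calendar time

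*SAP*

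**What the plan says.** The Phase I secondary objective explores clinical events before a change from the index anticoagulant. SAP section 8.4 counts "occurrence of any event listed below within 30 days before treatment interruption, switch, or discontinuation". Some of these events count only if they are new. The SAP puts it this way: "A new clinical event will be considered 'new' when it occurs for the first time within a 6-month period for acute conditions", and it sets the window at "5-years for chronic conditions (cancer, chronic kidney disease, and liver disease"). Protocol section 9.3 has the same rule.

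The data span is fixed elsewhere. SAP section 7 uses the claims database "between 1 Mar 2012 and 31 Dec 2019 to identify all variables (exposure, outcome, covariates"). Protocol section 10.3 confirms that nothing earlier is requested: "We will obtain a customized HIRA database between 1 Mar 2012 and 31 Dec 2019". On accrual, SAP section 8.2 says: "The study cohort will be defined as patients diagnosed with VTE between 1 Mar 2013 and 30 Jun 2019".

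SAP section 10 presents treatment-pattern results by index anticoagulant and repeats the analyses for each NOAC. Neither document says how to classify a chronic diagnosis with less than five years of history. Protocol section 9.9 (limitations) does not mention it, and no sensitivity analysis varies this window. The SAP's lists of tables and figures name no output for this objective.

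**The concern.** Accrual opens one year after the data begin. That suits the 12-month washouts for VTE and anticoagulants and the 6-month window for acute conditions, but not a 5-year window. A program applying the rule to this extract will look back as far as the data go. A kidney, liver or cancer diagnosis that predates the visible history then passes as new.

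A shorter look-back can only increase this error, and the look-back lengthens with calendar time. Drug choice also changed over calendar time: the SAP introduction says "All NOACs became available as the first-line treatment of acute VTE in Korea after reimbursement expansion in May 2015". Results shown by index anticoagulant could therefore differ in the frequency of chronic triggers partly because their data windows differ. A reader could take that for a difference in why patients change treatment.

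**Working it through.** The documents give no figure to reproduce for this objective. The check is calendar arithmetic.

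**Inputs.** Data start: 1 March 2012 (SAP 7, protocol 10.3). Accrual: 1 March 2013 to 30 June 2019, which is 2,313 days (SAP 8.2). Data end: 31 December 2019. Required look-back: 5 years (SAP 8.4).

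**First date with a full look-back.** 1 March 2012 + 5 years = 1 March 2017.

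**Share of calendar time without it.**
- Index dates before 1 March 2017: 1,461 / 2,313 = 63.2%.
- Time in which a treatment change can fall (1 March 2013 to 31 December 2019, 2,497 days): 1,461 / 2,497 = 58.5%.

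**Anchoring on treatment change.** The event window precedes the change, not the index date. With a lag of L days from index to change and uniform accrual (assumption), the share of index dates lacking five years is (1,461 − L) / 2,313:

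| Lag | Calculation | Share |
|---|---|---|
| 3 months (90 days) | 1,371 / 2,313 | 59.3% |
| 6 months (180 days) | 1,281 / 2,313 | 55.4% |
| 9 months (270 days) | 1,191 / 2,313 | 51.5% |
| 12 months (365 days) | 1,096 / 2,313 | 47.4% |

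If patient numbers grow over time (assumption), later dates weigh more:

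| Annual growth | Lag 0 | Lag 3 months | Lag 6 months |
|---|---|---|---|
| 10% | 56.0% | 51.9% | 47.9% |
| 20% | 49.4% | 45.2% | 41.2% |

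**How short the look-back becomes.** Measured at index and capped at 5 years:
- Index before May 2015: 1.0 to 3.2 years, mean 2.1.
- Index May 2015 to February 2017: mean 4.1 years.
- Index from March 2017: 5 years.

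If treatment changes soon after a March 2013 index date, the 30-day window can reach back before index and leave only about 11 months.

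**Effect on misclassification (illustration only).** Assume that a patient with existing disease generates claims for it at rate r per year. The chance that none is visible in a look-back of L years is exp(−rL):

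| r per year | 1 year | 2 years | 5 years |
|---|---|---|---|
| 0.5 | 61% | 37% | 8% |
| 1 | 37% | 14% | 0.7% |
| 2 | 14% | 1.8% | about 0% |

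The direction is fixed, but the size runs from large to negligible with r, which the documents do not give.

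**Link to drug.** The 2018 sample in SAP section 9 has 83 + 264 + 57 + 26 = 430 NOAC starters. Its pairwise comparisons show 118 to 129 warfarin starters. Warfarin is then 118/548 to 129/559, or about 22% to 23% of oral anticoagulant starters late in the study.

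**The case against.** The best defence is that the rule still runs, as a look-back of up to five years, and that little depends on it. The objective is exploratory, Phase I has no prespecified hypotheses, and no test is specified for these events. This stands as a limit on scope. It does not settle the point, because the rule as applied is not the rule as written and neither document discloses the difference.

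The cancer event is also partly protected: it needs a cancer code with a V code and applies only to patients without active cancer at index. That protection is incomplete. V-code registration lasts five years or longer, so a patient diagnosed before the data begin, and untreated in the six months before index, can have a later V-coded claim that looks new.

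A reader might go further and infer that warfarin patients have 1.0 to 3.2 years of look-back and NOAC patients 3.2 years or more. The documents do not support that. It compares a calendar group with a drug group. Warfarin starts continue into 2018, the introduction does not say that no NOAC was used before May 2015, and NOAC starters before March 2017 are truncated too. Nor can the inference be extended to PAC-only patients, for whom the documents give no numbers in any year.

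Finally, misclassification figures for a one-year look-back describe only the earliest index dates. They are chances that old disease was not visible earlier, not shares of reported events.

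**Conclusion.** The point holds on the documents' own dates. The 5-year rule cannot be met for any event before 1 March 2017: 63% of index calendar time, or about 47% to 59% of index dates if treatment changes 3 to 12 months after index under uniform accrual. Growth in patient numbers lowers these shares. Truncation makes some existing kidney disease, liver disease and cancer count as new, more so in earlier years.

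That this weighs more on warfarin than on NOAC starters is probable, given the May 2015 expansion and the 2018 mix. Without a yearly drug mix the size of the difference cannot be derived. The acute conditions, with their 6-month window, and the Phase II major-bleeding comparison are not affected. The correction should be made but is not critical.

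**What to change.** In SAP section 8.4 and protocol section 9.3:

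1. State that the look-back for chronic conditions is up to 5 years, limited by data from 1 March 2012.
2. Report new chronic events by index treatment under the full 5-year definition only for treatment changes on or after 31 March 2017. The 30-day window then starts no earlier than 1 March 2017, so all of it has five years of history.
3. For the full cohort, add an analysis with a uniform 12-month look-back, counting only events on or after the index date. Every patient has that history because accrual starts on 1 March 2013.

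This needs a short change of definition and two added outputs, but no new data. The restricted analysis uses fewer patients: it covers 1,006 of the 2,497 days in which a change can occur (2,497 − 1,461 − 30 = 1,006), or 40%. The 12-month version labels more old disease as new. It equalises the look-back, not the misclassification, which still depends on how common each disease is in each group. It should therefore accompany the restricted analysis, not replace it.

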7. RATIONALE AND BACKGROUND

Venous thromboembolism (VTE) is a disorder that includes deep vein thrombosis (DVT) and pulmonary embolism (PE). Of VTE, DVT occurs when a blood clot forms in a deep vein, usually in the lower leg, thigh, or pelvis and PE occurs when a clot breaks loose and travels through the bloodstream to the lungs to eventually block an artery in the lung. Blood clots can develop in veins when damaged by surgery or trauma, or because of an inflammation in response to an infection or injury. Other risk factors for VTE include a history of a previous VTE event, comorbidities such as cancer or spinal cord injury, pregnancy, paralysis or long periods of immobilization, specific genes, and certain circumstances related to age, race, and sex. As a previous VTE event is a strong risk factor for the onset of VTE, recurrence of VTE is common, with a previous study reporting that approximately 30% of patients who experienced VTE will develop recurrent VTE within 10 years of their initial event [1]. With high rates of recurrence and mortality, as well as increased long-term morbidity and functional disability, VTE remains a major public health concern with a substantial disease burden [2] [3].

For pharmacologic treatment of patients with VTE without cancer, the American College of Chest Physicians (CHEST) guidelines recommend the use of non-vitamin K antagonist oral

anticoagulants (NOACs) over Vitamin K Antagonists (VKAs), with supporting evidence suggesting that each NOAC (e.g., apixaban) is effective at preventing recurrent VTE [4]. More recently, in the treatment guidelines for management of VTE released by the American Society of Hematology (ASH), NOACs are still recommended over VKAs for the initial management of VTE [5].

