- Overall anticoagulant treatment duration will be defined as the time period from the index date to the earliest of treatment interruption, switch, or discontinuation.
- If a patient has evidence of a repeat prescription within 30 days of the end of their prescription and does not experience any of the above events (treatment interruption, switch, or discontinuation), they will be assumed to be persistent on treatment.[21]
- Clinical event preceding first treatment change will be defined as occurrence of any event listed below within 30 days before treatment interruption, switch, or discontinuation. A new clinical event will be considered 'new' when it occurs for the first time within a 6-month period for acute conditions (arterial

thromboembolism, ischemic stroke, transient ischemic attack, myocardial infarction, angina pectoris, acute kidney injury, and abnormal liver function) and 5-years for chronic conditions (cancer, chronic kidney disease, and liver disease). A patient may contribute to multiple events.

- ① Major bleeding (as defined in Table 2)
- ② Complications of VTE: post-thrombotic syndrome and chronic thromboembolic pulmonary hypertension
- ③ Thromboembolism: PE diagnosis in patients with index event as DVT only, new diagnosis of arterial thromboembolism, ischemic stroke, transient ischemic attack, myocardial infarction, or angina pectoris
- ④ Major surgery: orthopedic surgeries (knee arthroplasty, hip arthroplasty, and hip fracture surgery), cancer surgeries (stomach, colorectal, hepatobiliary, pancreatic, breast, ovarian, cervical, renal, bladder, prostate, lung, and esophageal cancers, and brain tumors), and benign surgeries (myomectomy, oophorectomy, and transurethral resection of the prostate)
- ⑤ Cancer-related event (among non-active cancer patients only): new diagnosis of active cancer
- ⑥ Kidney function change: new diagnosis of chronic kidney disease or acute kidney injury
- ⑦ Liver function change: new diagnosis of liver disease or abnormal liver function

- **Phase II of the study**

- Major bleeding will be defined using primary or secondary diagnosis codes according to the ICD-10 diagnostic codes shown in Table 2 and classified by site (intracranial, gastrointestinal [GI], and other sites) [22].

Table 2. Definition of major bleeding by site

Major bleeding	ICD-10 diagnosis code	Diagnostic definition

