*Blood transfusion (Korean Procedure Codes: X1001, X1002, X2011, X2012, X2021, X2022, X2031, X2032, X2041, X2042, X2051, X2052, X2061, X2062, X2071, X2072, X2081, X2082, X2091, X2092, X2101, X2102, X2111, X2112, X2121, X2122, X2131, X2132, X2141, X2142, X3010) will also be used to define other site bleeding history.

- Initial presentation of VTE
 - DVT (I80.2, I80.3)

- PE (I26.0, I26.9)
- Both DVT and PE
- Comorbidities (ICD-10 diagnostic code) will be measured within the 6-month period prior to the index date.
 - Antiphospholipid syndrome (D68.6, I82.9): As diagnosis of antiphospholipid syndrome is usually made after VTE diagnosis with subsequent diagnostic procedures, its presence will be evaluated within the 6-month period after the index date.
 - Asthma (J45)
 - Cancer (C00-C97): History of cancer (non-active) will be evaluated within a lifetime prior to the index date.
 - Chronic obstructive pulmonary disease (COPD; J40-J44)
 - Chronic kidney disease (N18, N19)
 - Chronic liver disease (B18, B19, K70-K77)
 - Diabetes mellitus (E10-E14)
 - Fracture (S22, S32, S42, S52, S62, S72, S82, S92, T10, T12)
 - Heart failure (I50)
 - Hyperlipidemia (E78)
 - Hypertension (I10-I15)
 - Ischemic heart disease (I24, I25)
 - Myocardial infarction (I21)
 - Stroke (I60-I64, I69, G45)
 - Trauma (T79, T98, V01–V99, W11–W17, W50–W52, W64, X34–X39, Y01–Y04, Y30–Y32)
- Previous use of medications (WHO-ATC code) will be measured within the 6-month period prior to the index date.
 - Corticosteroids (H02)
 - Nonsteroidal anti-inflammatory drugs (NSAIDs; M01A)
 - Angiotensin-converting enzyme (ACE) inhibitors (C09A, C09B)

- Angiotensin II receptor blockers (ARBs; C09C, C09D)
- Antiplatelet agents (aspirin [N02BA01], aspirin/dipyridamole [B01AC30], abciximab [B01AC13], beraprost [B01AC19], cilostazol [B01AC23], clopidogrel [B01AC04], iloprost [B01AC11], indobufen [B01AC10], limaprost [C04AX], ozagrel [R03DX], prasugrel [B01AC22], sarpogrelate [B01AC], ticagrelor [B01AC24], ticlopidine [B01AC05], tirofiban [B01AC17], treprostinal [B01AC21], triflusal [B01AC18])
- Azole antifungal agents (fluconazole [J02AC01], itraconazole [J02AC02], voriconazole [J02AC03], posaconazole [J02AC04])
- β -blockers (C07)
- Calcium-channel blockers (C08)
- Selective serotonin reuptake inhibitors (SSRIs; N06AB)
- Proton pump inhibitors (PPIs; A02BC)
- Diuretics (C03)
- Thiazides (C03A)
- Vasodilators (C01D, C04A)
- Estrogens (G03C)
- Cyclooxygenase (COX)-2 inhibitors (M01AH)

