- In the NOAC-based group, all analyses will be repeated stratified by each individual NOAC class (e.g, apixaban, dabigatran, rivaroxaban, edoxaban) to

PFIZER CONFIDENTIAL

identify the difference in baseline characteristics and treatment patterns between each NOAC class.

- To identify potential reasons for treatment change, clinical events preceding the first treatment change (major bleeding, thromboembolism diagnosis, complications of VTE, major surgery, active cancer, a new diagnosis of CKD or AKI, a new diagnosis of liver disease or abnormal liver function) will be measured within 30 days prior to the first date of treatment change. Patients can contribute with multiple events.
- All analyses of treatment patterns will be presented stratified according to the index anticoagulant treatment, and not overall or per drug class.

Phase II of the study (comparative)

Propensity score analysis

- To balance and adjust for any potential differences in baseline sociodemographic and clinical characteristics between treatment groups, propensity score (PS) methods will be implemented.
 - A logistic regression model will be used to estimate the predicted probability (propensity) of initiating each NOAC compared with warfarin given baseline covariates mentioned above. By using the estimated PS, we will apply the PS based on the inverse probability of treatment weights (IPTW), where the treatment group of interest will be given a weight of 1/PS, and the comparator group will be given a weight of 1/(1-PS) [4, 5]. The most extreme 1% of PS values (IPTW with trimming) will be excluded to improve comparability between exposure groups.

Main Analysis

- Sociodemographic and clinical characteristics will be summarized with means (STD) or median (IQR) for continuous variables and with count (proportions) for categorical variables for the two treatment comparisons of: apixaban vs warfarin, rivaroxaban vs warfarin, edoxaban vs warfarin and dabigatran vs warfarin (and NOAC vs NOAC, if scientifically feasible).
 - Differences in baseline covariates between users of different OACs will be assessed using the SD where the absolute SD <0.1 will be considered as well balanced.
- The incidence rate of major bleeding overall and by site will be presented as the total number of events per 1,000 person-years, with its 95% CIs estimated using the Poisson distribution.

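### The 'thromboembolism' event before treatment change counts a venous event only as PE in DVT-only patients, so it under-records VTE treatment failure and cannot show it in PE-index patients

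*SAP*

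**What the plan says.** The Phase I secondary objective is to explore clinical events that come before a change from the index anticoagulant. SAP 10 and Protocol 9.7 give the purpose as finding potential reasons for the change. The window is the 30 days before the first interruption, switch or discontinuation.

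- **Thromboembolism item (SAP 8.4):** "PE diagnosis in patients with index event as DVT only, new diagnosis of arterial thromboembolism, ischemic stroke, transient ischemic attack, myocardial infarction, or angina pectoris". Protocol 9.3 has the same restriction: "PE diagnosis in patients with index event as DVT only".
- **Codes (SAP 8.4 table):** I26.0 and I26.9 for PE. The item's other codes are I74, I63, G45.9, I21 and I20.
- **The other VTE-related item:** "Complications of VTE: post-thrombotic syndrome and chronic thromboembolic pulmonary hypertension", coded I87.0 and I27.2.
- **DVT codes:** the SAP defines index DVT as "DVT (I80.2, I80.3") and uses the same two codes for inclusion and exclusion. They appear in no preceding-event row.
- **Presentation (SAP 10):** "All analyses of treatment patterns will be presented stratified according to the index anticoagulant treatment, and not overall or per drug class". No split by index event is planned for the preceding events, and none of the SAP table shells 1 to 20 displays them.

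Neither document explains the restriction to DVT-only patients, and Protocol 9.9 does not list it as a limitation.

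**The concern.** All patients are anticoagulated for VTE, so a new venous event on treatment is the most direct effectiveness reason to change drug. An event list meant to find such reasons should be able to see it, or should say that it cannot. As defined, a reader of the final report could take a low thromboembolism figure to mean that recurrent VTE rarely precedes a treatment change. The definition cannot support that conclusion.

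There is also a comparability problem. The PE component can occur only in DVT-only patients. If its denominator is everyone on an index drug, the figure depends on how many of that drug's users had PE at index, whatever the drug's effect. The cancer item is also restricted to a subset, but Phase I is analysed separately by active cancer, so that item's denominator matches. The thromboembolism item has no such matching split.

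**Working it through.** The plan states no rate, count or power for this item, so there is no figure to reproduce. The check is a cross-tabulation of the definition, followed by two illustrations on assumed inputs.

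**1. What can be recorded.** Index presentation (SAP 8.4) is DVT only, PE only, or both. The later venous event is DVT (I80.2, I80.3) or PE (I26.0, I26.9).

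| Index event | Later DVT | Later PE |
|---|---|---|
| DVT only | not counted | counted |
| PE only | not counted | not counted |
| DVT and PE | not counted | not counted |

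One cell in six is countable. The complications item does not fill the gap, because I87.0 and I27.2 code sequelae and share no code with DVT or PE.

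**2. Share of recurrent VTE that could be captured (assumed inputs, not in the documents).** If recurrence risk is the same for all index types, captured share = (share of patients with DVT-only index) × (share of their recurrences that are PE).

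- Low: 0.30 × 0.10 = 3%
- Middle: 0.50 × 0.30 = 15%
- High: 0.70 × 0.50 = 35%

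The share is low across this range, but not zero.

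**3. Effect of DVT/PE mix on a comparison by drug (assumed inputs).** Suppose 2% of DVT-only patients on either drug have a PE before change, and the denominator is all patients on the drug. PE component = 2% × (1 − PE share).

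| PE share, group A / group B | A | B | Ratio B/A |
|---|---|---|---|
| 60% / 40% | 0.8% | 1.2% | 1.50 |
| 60% / 50% | 0.8% | 1.0% | 1.25 |
| 50% / 40% | 1.0% | 1.2% | 1.20 |
| 60% / 60% | 0.8% | 0.8% | 1.00 |

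This is the PE component alone. The whole item also contains arterial events, which any patient can have. Adding an equal assumed arterial rate to the 60/40 case, with no overlap:

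- 1%: 2.2 / 1.8 = 1.22
- 3%: 4.2 / 3.8 = 1.11
- 5%: 6.2 / 5.8 = 1.07

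The pooled item dilutes the distortion, but it also hides the venous events among strokes, infarctions and angina. With DVT-only patients as the denominator, the PE component is 2% in both groups whatever the mix.

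**The case against.** **The item does show treatment failure.** This is correct. A PE on anticoagulation in a DVT-only patient is a treatment failure and is counted. A reader might infer that the item can show no failure at all; the documents do not support that. It shows failure incompletely, and not at all in PE-index patients.

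**The missing newness rule does little harm.** The rule ("A new clinical event will be considered 'new' when it occurs for the first time within a 6-month period for acute conditions") names its acute conditions, and PE is not among them. A reader might infer that old PEs count as new. However, the first exclusion criterion removes anyone with a DVT or PE code in the 12 months before the index encounter, a longer look-back than the six months used for acute events. The rule's absence is therefore largely moot.

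**PEs found at work-up mostly do not count.** SAP 8.2 assesses initial presentation up to the index date, which is the first anticoagulant prescription. A PE coded before then makes the patient DVT and PE, and so ineligible. Only a PE coded after anticoagulant start and followed by a change within 30 days gets through. That route is narrow, but it is open.

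**The 1.5-fold ratio is an illustration.** It rests on an assumed 2% rate, assumed PE shares and an all-patient denominator that the plan does not state, and it excludes the arterial events. It is not an estimate of bias.

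**The restriction may be deliberate.** Repeat DVT or PE codes in claims can be the index event carried forward. This is plausible, but neither document says so. It argues for a careful recurrence definition or a stated limitation, not for silence.

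**The stakes are low.** The objective is exploratory and secondary, Phase I has no prior hypotheses, and no between-drug test is specified for this item. The Protocol's background remark that "recurrence of VTE is common" refers to about 30% within 10 years, not to recurrence on treatment shortly before a change. All of this stands, and it limits the importance of the point.

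**Conclusion.** The point holds in limited form. By definition, and without any assumption, recurrent PE in PE-index patients and recurrent DVT in any patient cannot be recorded as events preceding treatment change, and no other item captures them. The item under-records VTE treatment failure as a potential reason for change and cannot show it in PE-index patients.

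The comparability problem is conditional. It arises only if the item is reported over all patients by index drug and the drugs differ in DVT/PE mix. Its size is unknown before the data are seen, and it vanishes if the mix is equal. SAP Tables 1 to 4 will show the mix by treatment group and by NOAC.

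The consequence is confined to the exploratory Phase I secondary objective. The Phase II major-bleeding comparison does not depend on it. The plan should still be changed, because the change is cheap and alters what this analysis can be said to show.

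**What to change.** Amend SAP 8.4 and 10 and Protocol 9.3, 9.7 and 9.9 as follows.

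1. **Separate the PE component.** Report it apart from the arterial events, labelled *new PE in DVT-only index patients*, with DVT-only patients as the denominator. Count PE codes only after the index encounter ends, which closes the remaining work-up route.
2. **Add one item for all patients, labelled *VTE readmission*.** Define it as a new admission starting after the index encounter ends, with I26.0, I26.9, I80.2 or I80.3 as primary diagnosis. Show it by index event (DVT only; PE with or without DVT), the split already used in SAP Tables 1 to 4. The admission and primary-position requirements limit carried-forward codes; the plan already requires an admission code for major bleeding.
3. **State the limitation.** Recurrences managed without admission are missed, and some readmissions may carry the index code.
4. **Add a table shell** for the preceding events, with these denominators.

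If the sponsor judges item 2 unreliable in these claims, do item 1 and state that recurrent VTE is otherwise not assessed, so that a low thromboembolism figure must not be read as rare recurrence before treatment change.

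The cost is wording in two documents, one derived variable from claims already held, and one shell. The price of item 2 is imperfect capture in both directions, which is why its label should say readmission and not recurrence.
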